[figure not shown]
[figure not shown]

## CLINICAL TRIAL PROTOCOL SYNOPSIS

Company name	Boehringer Ingelheim
Protocol date	16 Jan 2020
Revision date	07 Oct 2022
BI trial number	1436-0001
Title of trial	A First-in Human trial to study safety and tolerability of single rising intravitreal dOses (open label, non-randomized, uncontrolled) and in addition the early biological response of multiple intravitReal dosing (single-masked, raNdomized, sham-controlled) of BI 764524 in panretinaL photocoagulation (PRP) treated proLiferative diabetic retinopathy (PDR) patients with diabetic macular ischemia (DMI) – the HORNBILL Study
Co-ordinating Investigator	 Phone:  Fax: 
Trial sites	Multi-centre trial
Clinical phase	I/IIa
Trial rationale	
Diabetic macular ischemia (DMI) is a chronic complication of diabetic retinopathy (DR), and can potentially lead to visual functional loss. Currently, there are no approved or effective treatments to prevent either onset or progression of DMI in laser-treated PDR patients.
 
As a transition from preclinical investigations to clinical development in this first-in human trial, the maximum feasible dose (MFD) of BI 764524 will be determined and safety, tolerability and early biological response will be investigated in DMI volunteer patients.
 
This trial will include patients affected by DMI with significant visual loss since intravitreal (IVT) injections in patients without the condition would not be considered ethically justifiable.

Trial objectives	The objective of this trial is to determine the maximum feasible dose (MFD) for further development of BI 764524 in patients with pan-retinal coagulation treated proliferative diabetic retinopathy (PDR) patients with diabetic macular ischemia (DMI) based on the primary endpoint occurrence of dose limiting events (DLE) during MFD evaluation period of 7 days (single rising dose (SRD)) or 28 days after last administration (multiple dosing (MD)) and to investigate the safety, tolerability and early biological response after IVT injections of BI 764524.
-------------------------	--

Trial endpoints	
Primary endpoint
 
SRD part:
 

• number of patients with dose limiting events (DLEs) from drug administration till day 8 (7 days after treatment).

 
MD part:
 

• number of patients with drug related adverse events (AEs) from drug administration till end of study (EOS)

 
Secondary endpoints:
 
SRD part:
 

• number of patients with drug related AEs at EOS

• number of patients with ocular AEs (eye disorders) at EOS

 
MD part:
 

• change from baseline of the size of the foveal avascular zone (FAZ) in optical coherence tomography angiography (OCTA) in superficial and combined vascular complex at Visit 5

• change from baseline of the size of the FAZ in optical coherence tomography angiography (OCTA) in superficial and combined vascular complex at Visit 7

• change from baseline of BCVA (best corrected visual acuity) at Visit 3

• change from baseline of BCVA at Visit 4

• change from baseline of BCVA at Visit 5

• change from baseline of BCVA at Visit 6

• change from baseline of BCVA at Visit 7

• change from baseline of Central retinal thickness (SD-OCT) at Visit 3

• change from baseline of Central retinal thickness (SD-OCT) at Visit 4

• change from baseline of Central retinal thickness (SD-OCT) at Visit 5

• change from baseline of Central retinal thickness (SD-OCT) at Visit 6

• change from baseline of Central retinal thickness (SD-OCT) at Visit 7

• number of patients with ocular AEs (eye disorders) at EOS

Trial design	This trial will consist of an SRD part followed by an MD part. SRD part will be non-randomized, open-label, and uncontrolled. MD part will be single-masked, randomized and sham-controlled (ratio 2:1).

Number of patients	Approximately 45 patients in total
total entered each treatment	Up to 15 patients in the SRD part (depending on the dose escalation) and 30 patients in the MD part.
Diagnosis	Pan-retinal photocoagulation (PRP) treated proliferative diabetic retinopathy (PDR) in patients with diabetic macular ischemia (DMI)
Main criteria for inclusion	Patients to be included are pan-retinal photo coagulation (PRP) treated proliferative diabetic retinopathy (PDR) patients with diabetic macular ischemia (DMI)
Test product	BI 764524, powder for solution for injection
dose	SRD part: [REDACTED], [REDACTED] and [REDACTED] (single doses)  MD part: The highest dose (e.g. [REDACTED]) (q4w) established as safe and tolerable during the SRD part
mode of admin.	Intravitreal
Comparator product	Not applicable
dose	Not applicable
mode of admin.	Not applicable
Duration of treatment	SRD part: single intravitreal dose  MD part: 3 intravitreal doses in 4-weekly intervals (q4w)
Statistical methods	Descriptive statistics will be provided for all endpoints.

## FLOW CHART I (SINGLE RISING DOSE PART)

Trial Periods	Screening Period	Treatment Visit	Follow-up period					End of study
			1	2	3	4	5	
Study Days	Duration 3 to 28 days	Day 1	4	8	15	29	57	99
Study Weeks			Week 1	Week 2	Week 4	Week 8	Week 14	
Time window for visits (days)		none	±1	±2	±2	±3	±7	±7
Informed consent	X							
Demographics	X							
Medical history	X							
Physical examination (including weight)	X	X 				X	X	X
Vital signs	X	X	X	X	X	X	X	X
Laboratory tests	X	X		X	X	X	X	X
12 lead-ECG 	X	X	X			X	X	X
Review of in-/exclusion criteria	X	X						
Dose Assignment		X						
IVT drug administration		X						
Pregnancy test 	X S	X s		X U	X U	X U	X U	X U
PK Sampling 		X	X	X	X	X	X	X
██████████		X			X	X		X
BCVA testing	X	X	X	X	X	X	X	X
SD-OCT	X	X	X	X	X	X	X	X
OCT Angiography	X	X	X	X	X	X	X	X
Fundus Photo	X	X		X	X	X	X	X
Slit lamp and intra-ocular pressure (IOP)	X	X	X	X	X	X	X	X
All AEs/SAEs/AESIs	X	X	X	X	X	X	X	X
Concomitant therapy	X	X	X	X	X	X	X	X
Completion of patient participation 								X

(1) Could be repeated as deemed necessary at investigator's discretion.

- () See Section [5.2.5](#); the ECGs are to be recorded shortly before the PK sampling at the respective time points, see Appendix [10.1](#)
- () Pregnancy testing: serum pregnancy test (XS) is done at screening and on day 1 if more than a week elapsed between screening and day 1, and at the other visits as a reflex when urine testing (XU) is positive.
- () See separate flow chart for PK and [REDACTED] sampling (Appendix [10.1](#)).
- () Completion of patient participation also needs to be completed if the patient withdraws prematurely following assignment to dose level (see Section [3.3.4](#))

## FLOW CHART II (MULTIPLE DOSING PART)

Trial Periods	Screening Period	Treatment Period			Follow-up Period		End of Study
		1 	2	3	4	5	
Study Day/ Week	Duration 3 to 28 days	1	29 Week 4	57 Week 8	85 Week 12	113 Week 16	155 Week 22
Time window for visits (days)		none	±3	±3	±7	±7	±7
Informed consent	X						
Informed consent Aqueous sampling (optional)	X						
Demographics	X						
Medical history	X						
Physical examination (including weight)	X				X		
Vital signs	X	X	X	X	X	X	X
Laboratory tests	X	X	X	X	X	X	X
12 lead-ECG 	X	X	X	X	X		
Review of in-/exclusion criteria	X	X					
Dose Assignment		X					
Randomization		X					
IVT drug administration/Sham injection		X	X	X			
Pregnancy test 	X S	X S	X U	X U	X U	X U	X U
██████████		X	X		X		
PK Sampling 		X	X	X	X	X	X
Optional Aqueous sampling 		X		X		X	X
BCVA testing	X	X	X	X	X	X	X
SD-OCT	X	X	X	X	X	X	X
OCT Angiography	X	X	X	X	X	X	X
Fundus Photo	X	X	X	X	X	X	X
Slit lamp and intra-ocular pressure (IOP)	X	X	X	X	X	X	X
██████████		X	X	X	X	X	X
All AEs/SAEs/AESIs	X	X	X	X	X	X	X
Concomitant therapy	X	X	X	X	X	X	X
Completion of patient participation 							X

- (1) Screening visit should be performed in two visits. After Informed consent is obtained, visual acuity testing, SD-OCT, OCT Angiography and fundus photography should be performed and sent to central reading service. If patient is eligible based on the results from the reading centre, the patient should return to complete the rest of the screening. In case of scheduling difficulty for certain patients, screening can be performed in one visit. If screening is done as one visit, fundus photography should be performed in line with other ophthalmological examinations.
- (2) See Section [5.2.5](#); the ECGs are to be recorded shortly before the PK sampling at the respective time points: Appendix [10.1](#)
- (3) Pregnancy testing: serum pregnancy test ( $X_S$ ) is done at screening and on day 1 if more than a week elapsed between screening and day 1, and at the other visits as a reflex when urine testing ( $X_U$ ) is positive.
- (4) See separate flow chart for PK, ██████ and aqueous sampling (Appendix 10.1)
- (5) Completion of patient participation also needs to be completed if the patient withdraws prematurely following assignment to dose level (see Section [3.3.4](#))

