13. Significant disease or other medical conditions\* (as determined by medical history, examination and clinical investigations at screening) that may, in the opinion of the investigator result in any of the following:
  - a. Put the patient at risk because of participation in the study
  - b. Influence the results of the study
  - c. Cause concern regarding the patient's ability to participate in the study
14. Known hypersensitivity to any of the ingredients used in the IMP formulation, or any of the medications used
15. Active intraocular inflammation in the study eye
16. Active infectious conjunctivitis in either eye

17. Women who are pregnant, nursing, or who plan to become pregnant while in the trial

\*e.g. cardiac (including tachycardia), gastro-intestinal, hepatic, renal, metabolic, dermatologic, neurological, haematological, oncological and psychiatric. Patients with malignancy for which the patient has undergone resection, radiation or chemotherapy within past 5 years. Patients with treated basal cell carcinoma or fully cured squamous cell carcinoma are allowed.

For study restrictions, refer to Section [4.2.2](#).

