### **5.2.4 Safety laboratory parameters**

Safety laboratory parameters to be assessed are listed in Table [5.2.4: 1](#). For the sampling time-points please see the [Flow Chart I](#) and [Flow Chart II](#). Patients do not have to be fasted for the blood sampling for the safety laboratory.

All analyses will be performed by a central laboratory, except urine pregnancy test which will be performed by the site staff. The respective reference ranges will be provided in the ISF. Instructions regarding sample collection, sample handling/ processing and sample shipping are provided in the Laboratory Manual in the ISF. The central laboratory will send reports to the investigator. It is the responsibility of the investigator to evaluate the laboratory reports. Clinically relevant abnormal findings as judged by the investigator will be reported as AEs (please refer to Section [5.2.6](#)).

In case the criteria for hepatic injury are fulfilled, a number of additional measures will be performed (please see Section [5.2.7.1.4](#)) and the DILI Checklist provided in the electronic data capture (EDC) system. The amount of blood taken from the patient concerned will be increased due to this additional sampling.

The central laboratory will transfer the results of the analysis to the sponsor.

If blood sampling for central laboratory at the trial site is not possible, safety laboratory analyses can be performed at a local laboratory. The results of the laboratory tests must be transferred to the investigator who ensures medical review and documents a clinically relevant safety issue as an adverse event. For minimum required safety laboratory parameters, see Table [5.2.4: 1](#).

Table 5.2.4: 1 Safety laboratory parameters – whole blood, serum or plasma

---

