**Clinical chemistry**

- Albumin
- Alkaline phosphatase -  $\gamma$ -GT (gamma-glutamyl transferase) reflex test triggered by elevated alkaline phosphatase on two sequential measures
- ALT (alanine aminotransaminase, SGPT)
- AST (aspartate aminotransaminase, SGOT)
- Bicarbonate
- Bilirubin total, fractionated if increased
- Calcium
- Chloride
- Creatinine
- Serum Pregnancy test\*
- Creatine kinase (CK)
- CK-MB, troponin I (reflex tests if CK is elevated)
- Lactate dehydrogenase (LDH)
- Lipase
- Magnesium
- Phosphate
- Potassium
- Protein total
- Sodium
- Urea (BUN)
- LDL/HDL and total cholesterol
- Triglycerides
- TSH
- Folate

---

\*Serum pregnancy test at screening and at visit 2 as well as confirmation of positive urine pregnancy test (only for WOCBP)

Table 5.2.4: 2 Safety laboratory parameters – urine

---

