#### Human urine chorionic gonadotropin (HCG)\*

---

\*Pregnancy testing (HCG, urine): performed on-site, see flow chart I and flow chart II (only for WOCBP)

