#### 6.2.1 Screening and run-in period(s)

##### Screening Period

The screening visit does not need to be done with the patient in a fasted state. All patients must sign an Informed Consent consistent with ICH GCP guidelines prior to any study specific procedures, this includes the option that the patient signs the Informed Consent during an extra contact to the study site prior to the actual screening visit. The patient should be recorded on the enrolment log as a screened patient when Visit 1 is performed. Visit 1 is the beginning of the screening period. As soon as eligibility of an enrolled patient is confirmed, the treatment visit (Visit 2) may be performed. If the patient does not meet inclusion/exclusion criteria, the patient must be recorded in the eCRF as a screen failure.

Applies to the SRD part: In case of closed dose groups no further rescreening activities for a screened and eligible patient are required within 12 weeks after completed screening visit. If screening visit has been performed earlier than 28 days before randomization, an additional visit for repeating of safety lab, vital signs, ECG and targeted physical examination has to be performed.

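### For women of childbearing potential screened more than a week before Day 1, the protocol does not provide for the Day 1 pregnancy result to be known before first injection, and two footnotes disagree on when that test is due

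*Protocol*

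**What the plan says.** **Exclusion.** Both parts exclude "Women who are pregnant, nursing, or who plan to become pregnant while in the trial" (Protocol 3.3.3, SRD criterion 13 and MD criterion 17).

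**Day 1 test.** In Flow Charts I and II the Day 1 cell for the pregnancy test carries only the serum symbol. Footnote 3, the same in both charts, says the serum test "is done at screening and on day 1 if more than a week elapsed between screening and day 1". Elsewhere after screening, serum is used only as a reflex to a positive urine test. The urine symbol appears only after Day 1, including at MD Visits 3 and 4, which are injection visits.

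**Where it is analysed.** Section 5.2.4: "All analyses will be performed by a central laboratory, except urine pregnancy test which will be performed by the site staff". There is a fallback: "If blood sampling for central laboratory at the trial site is not possible, safety laboratory analyses can be performed at a local laboratory".

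**Timing in the laboratory table.** The footnote to Table 5.2.4: 1 reads "Serum pregnancy test at screening and at visit 2 as well as confirmation of positive urine pregnancy test", with no condition on time since screening.

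**Sequence.** The screening period is given as "Duration 3 to 28 days". Section 6.2.1 says "As soon as eligibility of an enrolled patient is confirmed, the treatment visit (Visit 2) may be performed". Review of the criteria, dose assignment, randomisation (MD) and the first injection are all placed on Day 1, which has no visit window. Section 8.3.1 asks for documented evidence, before a patient is allocated to treatment, that every criterion is satisfied, and says that missing records do not make a patient eligible.

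**The concern.** Footnote 3 treats a screening result more than a week old as needing a repeat. The repeat is then a serum sample taken on the injection day and analysed by default at a central laboratory, and nothing says the site must have the result before it allocates and injects. A safeguard placed on the dosing day does its work only if it is read before dosing.

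The method also differs between injections without explanation. The second and third MD injections have an on-site test at the same visit. The first injection, which is the only one in the SRD part, does not.

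What is at stake is patient protection in a first-in-human trial. A positive result that arrived after an active injection would mean exposure during pregnancy, reportable within 24 hours (5.2.7.2.3). In the MD part the woman would already belong to the treated set (7.3) and would come off treatment, since pregnancy is a listed withdrawal reason (3.3.4.1). No sample size, error rate or planned analysis is affected; Section 7.2 plans no hypothesis tests.

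**Working it through.** The plan gives no figure to reproduce. The check sets the passages side by side and counts days.

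**1. Is a result available on Day 1 before injection?**

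| Visit with injection | Scheduled test | Where it is read |
|---|---|---|
| SRD Visit 2 (Day 1) | serum | central laboratory by default |
| MD Visit 2 (Day 1) | serum | central laboratory by default |
| MD Visit 3 (Day 29) | urine, serum if positive | on site |
| MD Visit 4 (Day 57) | urine, serum if positive | on site |

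The local-laboratory route opens only if central sampling is not possible at the site. Neither document states a turnaround time for the serum test or makes allocation or injection wait for its result. Section 8.3.1 sets the general requirement of documented eligibility but does not name the Day 1 test.

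**2. Which screening intervals are involved?** The inputs are a screening period of 3 to 28 days (flow charts) and a threshold of more than a week, read as 8 days or more.

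- All whole-day intervals: 28 − 3 + 1 = 26.
- No Day 1 test under footnote 3 (3 to 7 days): 7 − 3 + 1 = 5.
- Day 1 test required under footnote 3 (8 to 28 days): 28 − 8 + 1 = 21, and 5 + 21 = 26.

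These count possible intervals. They are not shares of patients, and the documents do not give the number of women of childbearing potential.

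**3. How old is the latest known result at first injection?** This depends on the turnaround, which has to be assumed.

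- Reported the same day: the Day 1 result could be known, provided the site waits for it.
- Reported the next day or later, MD part: the screening result is the latest one, 8 to 28 days old in women who need the repeat. This counts from the screening serum draw. MD screening should be split over two visits (Flow Chart II, footnote 1), and footnote 3 does not say which of them starts the week.
- Reported the next day or later, SRD part: the same range applies on the ordinary route. If a dose group is closed, Section 6.2.1 requires no rescreening for 12 weeks, but beyond 28 days it adds a visit that repeats the safety laboratory. Table 5.2.4: 1 lists the serum pregnancy test among safety laboratory parameters, while its footnote ties that test to screening and Visit 2. The latest result could therefore be newer or older than the ordinary range, depending on how that is read.

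**4. Do the two footnotes agree?** For a woman screened 3 to 7 days before Day 1, footnote 3 calls for no Day 1 test and the footnote to Table 5.2.4: 1 calls for one. The two conflict in 5 of the 26 intervals and agree in the other 21. This step needs no assumption about turnaround.

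**The case against.** A reader might infer that the Day 1 result cannot be known before the injection, and that the pregnancy exclusion therefore cannot be applied at first dosing. The documents do not support that. No turnaround time is stated, shipping details are left to a Laboratory Manual, and a conditional local-laboratory route exists. A serum test is mandatory at screening, eligibility is confirmed before Visit 2 may take place, and the criteria are reviewed again on Day 1. Two methods of contraception are required from Visit 1 (4.2.2.3). The exclusion can be applied on the screening result.

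Section 8.3.1 is the best answer to the concern, because a careful site could read it as requiring the Day 1 result before allocation. It does not say so, however, and it gives no means of obtaining the result in time.

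Three further points limit the consequence. The MD part randomises 2:1, so one third of its patients receive sham and would not be exposed to the drug. No endpoint or analysis changes. The SAP (6.1) records recruitment as completed, so an edit cannot alter how these patients were dosed and would serve the record and any later protocol built on the same flow chart.

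What remains is the missing provision for a current result before first dosing, and the contradiction between the footnotes.

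**Conclusion.** The point holds in a limited form. For women of childbearing potential screened more than a week before Day 1, the protocol calls for a repeat pregnancy test but does not provide for its result to be available before same-day allocation and first injection. The exclusion stays operable on the screening serum result; what is missing is confirmation by a current one.

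The size rests on one assumption, that a centrally analysed sample is not reported on the day it is drawn. If so, the latest known result in the MD part is 8 to 28 days old; in the SRD part the closed-dose-group rule can change that range. If results do come back the same day, the gap closes only where the site waits, which no text expressly requires for this test.

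The contradiction between footnote 3 and the footnote to Table 5.2.4: 1 stands whatever the turnaround. This is a worthwhile, inexpensive correction to an eligibility safeguard, with no bearing on the statistical results.

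**What to change.** Reconcile footnote 3 of both flow charts, Section 5.2.4, the footnote to Table 5.2.4: 1 and Section 8.3.1 so that:

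- a current pregnancy result is documented before Day 1 allocation and injection. One way is to schedule on Day 1, in addition, the on-site urine test the protocol already uses at MD Visits 3 and 4, and to keep the serum test. Whichever route the sponsor chooses, the text should say that the result is read before allocation;
- one condition for the Day 1 test is stated, identically in the flow charts and the laboratory table. Which of the two existing conditions applies is for the sponsor to decide.

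The cost of the example is one extra on-site urine test per woman of childbearing potential, at a visit that already takes place and with a test the sites already perform. Otherwise the change is a flow chart entry and footnote wording.

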## ABBREVIATIONS

ADCC	Antibody-dependent cellular cytotoxicity
AE	Adverse event
AESI	Adverse events of special interest
ALCOA	Attributable, legible, contemporaneous, original and accurate
AUC	Area under the curve
AUC 0-∞	Area under the concentration-time curve of the analyte in serum over the time interval from 0 extrapolated to infinity
%AUC tz-∞	Percentage of AUC 0-∞ obtained by extrapolation
AUC t1-t2	Area under the concentration-time curve of the analyte in serum over the time interval t 1 to t 2
AUC 0-tz	Area under the concentration-time curve of the analyte in serum over the time interval from 0 to the last quantifiable data point
BA	Bioavailability
BCVA	Best corrected visual acuity
BI	Boehringer Ingelheim
BIPI	Boehringer Ingelheim Pharmaceuticals Inc.
BLRM	Bayesian logistic regression model
BP	Blood pressure
CA	Competent authority
CDC	Copper diethyldithiocabamate
CDISC	Clinical Data Interchange Standards Consortium
CI	Confidence interval
CL/F	Apparent clearance of the analyte in serum after extravascular administration
C max	Maximum measured concentration of the analyte in serum
CTM	Clinical Trial Manager
CRA	Clinical Research Associate
CRC	Central Reading Center
CRF	Case Report Form, paper or electronic (sometimes referred to as 'eCRF')
CRO	Contract Research Organisation
CST	Central subfield thickness
CT	Clinical trial
CTCAE	Common Terminology Criteria for Adverse Events
CTP	Clinical trial protocol
CTR	Clinical trial report
DILI	Drug induced liver injury

DLE	Dose limiting event
DME	Diabetic macular edema
DMI	Diabetic macular ischemia
DNA	Deoxyribonucleic acid
DR	Diabetic retinopathy
DRIL	Disorganisation of retinal inner layer
ECG	Electrocardiogram
EMA	European Medicines Agency
eCRF	Electronic case report form
eDC	Electronic data capture
EOS	End of study
ETDRS	Early treatment diabetic retinopathy study
EudraCT	European Clinical Trials Database
EWOC	Escalation with overdose control
F	Absolute bioavailability factor
FA	Fluorescein angiography
FAZ	Foveal avascular zone
FSH	Follicle stimulating hormone
GCP	Good Clinical Practice
gMean	Geometric mean
GMP	Good Manufacturing Practice
HCG	Human chorionic gonadotropin
HR	Heart rate
IB	Investigator's brochure
ICF	Informed Consent Form
ICH	International Conference on Harmonization
IEC	Independent Ethics Committee
IMP	Investigational Medicinal Product
IOP	Intra-ocular pressure
IPD	Important protocol deviation
IQRMP	Integrated Quality and Risk Management Plan
IRB	Institutional Review Board
IRT	Interactive response technology
ISF	Investigator site file
IUD	Intrauterine device
IUS	Intrauterine hormone-releasing system
IV	Intravenous
IVT	Intravitreal

$\lambda_z$	Terminal rate constant of the analyte in serum
LPLT	Last patient last treatment
MedDRA	Medical Dictionary for Regulatory Activities
MoA	Mode of Action
MD	Multiple dosing
MRT ex	Mean residence time of the analyte in the body, extravascular
MFD	Maximum feasible dose
NOAEL	No observed adverse effect level
OCT	Optical coherent tomography
OCTA	Optical coherent tomography angiography
OIR	Oxygen induced retinopathy
OPU	Operative unit
PD	Pharmacodynamic(s)
PDR	Proliferative diabetic retinopathy
PE	Polyethylene
PfOS	Powder for reconstitution of an oral solution
PIB	Powder in the bottle
PK	Pharmacokinetic(s)
PKS	Pharmacokinetic set
PP	Polypropylene
PR	Pulse rate
PRP	Panretinal photocoagulation
QT	Time between start of the Q-wave and the end of the T-wave in an electrocardiogram
QTc	QT interval corrected for heart rate using the method of Fridericia (QTcF) or Bazett (QTcB)
R	Reference treatment
REP	Residual effect period
RR	Respiratory rate
SAE	Serious adverse event
SCR	Screening
SD-OCT	Spectral domain optical coherence tomography
SMC	Safety monitoring committee
SOP	Standard operating procedure
SRD	Single-rising dose
ss	(at) steady state
SUN	Standardization of Uveitis Nomenclature

SUSAR	Suspected unexpected serious adverse reaction
SVC	Superficial vascular complex
T	Test product or treatment
$t_{\lambda_z, \text{start}(\text{end})}$	Lower (upper) limit on time for values to be included in the calculation of $\lambda_z$
TMF	Trial master file
$t_{1/2}$	Terminal half-life of the analyte in serum
$t_{\text{max}}$	Time from (last) dosing to the maximum measured concentration of the analyte in serum
$t_{\text{max}(,N)}$	Time from (last) dosing to the maximum measured concentration of the analyte in serum (after administration of N doses)
TS	Treated set
TSAP	Trial statistical analysis plan
$t_z$	Time of last measurable concentration of the analyte in serum
ULN	Upper limit of normal
$V_z/F$	Apparent volume of distribution during the terminal phase after extravascular administration
VA	Visual Acuity
VEGF	Vascular endothelial growth factor
WG	Working group
WOCBP	Women of childbearing potential
YAG	Yttrium aluminum garnet

